12. **Coagulation:** Should include Prothrombin Time (PT) or International Normalized Ratio (INR) and Partial Thromboplastin Time (PTT). Samples will be analyzed locally.
13. **Cardiac Troponin:** For participants undergoing screening, circulating levels of cardiac Troponin-I (cTnI) must be measured and found to be within the normal reference range within 28 days before study entry, preferably using the central laboratory kits provided. See [Section 7.1.7](#) for full details.
14. **Urinalysis:** Dipstick is acceptable. Microscopic analyses if dipstick abnormal. Samples will be analyzed locally.
15. **Triplicate 12 leads ECGs:** At each time point, three consecutive 12-lead ECGs will be performed approximately 2 minutes apart to determine mean QTcF interval. If the mean QTcF is prolonged (>500 msec), the ECGs should be re-evaluated by a qualified person at the institution for confirmation. Additional triplicate ECGs may be performed as clinically indicated.
16. **Registration:** Participant number and dose level allocation operated by Pfizer Inc.
17. **Investigational Product Administration:** Treatment to be administered after all other assessments required on that day have been performed.
18. **Tumor Assessments:** Tumor assessments will include all known or suspected disease sites. Screening images may be obtained within 5 weeks of registration. Imaging obtained as part of standard of care but within 28 days (-7 days) of registration may be used for screening assessment. Imaging may include chest, abdomen and pelvis CT or MRI scans or bone scans. Bone scans will be performed at baseline if disease is suspected and on-study as appropriate to follow disease. Baseline central nervous system (CNS) imaging is not required with the exception of symptomatic participants to rule out CNS metastases. CT or MRI scans, as well as bone scans, when indicated, are to be done every 8 weeks ( $\pm$  5 days) with the first one to occur 8 weeks after C1D1 until disease progression that requires new treatment modality, permanent discontinuation, or death. Disease progression will be confirmed with two consecutive timepoints at least 4-6 weeks apart in the absence of rapid clinical deterioration. Tumor assessment should be repeated at the End of Treatment visit if more than 6 weeks have passed since the last evaluation. **CCI** [REDACTED]  
[REDACTED]  
[REDACTED]

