6.5. Part B Secondary Endpoint

- *For Cohort 3B: Objective response rate (ORR) and duration of response, as assessed using the Response Evaluation Criteria in Solid Tumors (RECIST) version 1.1.*
- *For Cohort 3B: Antitumor response and tumor control duration based on total measurable tumor burden as assessed by the Immune-Related Response Criteria Derived from RECIST 1.1 (irRECIST).*
- *For Cohort 3B: Bone outcome according to Prostate Cancer Working Group 3 (PCWG3) criteria.*
- *For Cohort 3B: Radiographic Progression-Free Survival (rPFS) by RECIST 1.1, irRECIST and PCWG3 Criteria in participants with mCRPC.*
- *PSA-50 response rate and duration of response.*
- *Baseline and changes from baseline for PSA, PSA velocity, PSA slope and PSA doubling time (PSADT).*
- *Trough concentrations after multiple dosing (C_{trough}).*
- *C_{trough} after multiple dosing.*
- *Incidence and titers of ADA and neutralizing antibodies against tremelimumab.*
- *Incidence and titers of ADA and neutralizing antibodies against PF-06801591.*

CCI

- 
- 
- 
- 
- 
- 
- 
- 

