Selected ad-hoc efficacy analyses (eg, ORR and radiographic PFS) combining participants from Cohorts 7A and 3B may be conducted, as participants in those two cohorts have identical or similar eligibility criteria for study entry and are scheduled to receive the same regimen.

Swimmer plots may be used to display duration of treatment and tumor response at each applicable time point. Waterfall plot for individual tumor size percent change from baseline, and spider plot for individual tumor size percent change from baseline over time may be presented. These plots, if generated, will be presented for RECIST 1.1 and irRECIST separately.

For the rPFS analysis in Part B, the Kaplan-Meier analysis may be performed if deemed necessary. If the Kaplan-Meier analysis is performed for radiographic progression-free survival, an event is defined as the first occurrence of “PD” status by investigator, or death, or a PCWG3 defined bone disease progression, whichever comes first, under RECIST. Time zero for all time-to-event analyses will be defined as the first vaccination on Cycle 1 Day 1. This analysis may be performed for the combined cohorts 7A and 3B. CCI

For duration of response per RECIST and time to response (from the first vaccination date to the time of the first response, CR or PR) in Part B, descriptive statistics will be provided. Kaplan-Meier analysis may be performed if deemed necessary. These analyses may be performed for the combined cohorts 7A and 3B.

PSA kinetics

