PSA, PSA velocity, PSA slope and PSA doubling time (PSADT); PSA will be provided from laboratory data. PSA velocity is defined as the slope of the linear regression line of PSA against time in month. PSA slope is the slope of the linear regression line of natural log of PSA against time in month. PSA doubling time is defined as the natural log of 2 divided by the slope of the linear regression line of the natural log of PSA against time in month (see 10.2). These analyses will be conducted both for Central PSA and Local PSA in separate tables. PSA kinetics will be presented at individual level by timepoint (listings and plots). Mean % and absolute change from baseline in PSA kinetics may be presented by cohort. To report PSA-based outcomes, PCWG3 recommends that the percentage of change in PSA from baseline, as well as the maximum decline in PSA, PSA velocity, PSADT and PSA slope that occurs at any point after treatment be reported for each patient using a waterfall plot. Waterfall plots provide a broader and more sensitive display of data, and are more informative until a validated surrogate of clinical benefit is available.

A PSA-50 response rate may be calculated by cohort. PSA-50 response rate is defined as the proportion of patients whose on-study PSA declined from baseline by at least 50% at two consecutive measurements at least 3 weeks apart, prior to other systematic anti-cancer therapy. For the subset of PSA-50 responders, a duration of PSA-50 response will be summarized. Duration of PSA-50 response is defined as the period between the first

measurement when PSA-50 response was achieved to the measurement when PSA-50 response no longer holds.

Swimmer plots may be used to display duration of treatment and PSA values at each applicable time point.

CTC

The frequency of “traditional” and “all candidate” CTCs in whole blood each expressed as CTC/mL will be assessed in pre treatment (Screening, Cycle 1 Day 1) and post treatment (eg. Cycle 1 Day 71, Cycle 2 Day 1, Cycle 2 Day 29, Cycle 2 Day 99, and End of Treatment) samples. Analysis of the CTC endpoints may include absolute CTC and fold-change from baseline (pretreatment) by patient and % change and mean fold-change by cohort.

MDSC

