Immune-related DC rate (irDCR) is the proportion of patients with irDC.

Immune-related Duration of Response (irDR) is defined, for patients with an immune-related objective response, as the time from first documentation of immune-related objective response (irCR or irPR) to the date of first documentation of irPD (which is subsequently confirmed) or death due to any cause. If a patient has not had an event (irPD or death), irDR is censored at the date of last adequate tumor assessment. The censoring rules for irDR are as described below for irPFS.

$$\text{irDR (months)} = [\text{date of event or censoring} - \text{first date of irOR} + 1]/30.4375$$

Immune-related Time to response (irTTR) is defined, for patients with an irOR, as the time from the start date to the first documentation of immune-related objective tumor response (irCR or irPR) which is subsequently confirmed.

$$\text{irTTR (in months)} = [\text{first date of irOR} - \text{start date} + 1]/30.4375$$

Immune-related Progression-Free Survival (irPFS) is defined as the time from start date to the date of irPD or death due to any cause, whichever occurs first. irPFS data will be censored on the date of the last adequate tumor assessment for patients who do not have an event (confirmed irPD or death), for patients who start a new anti-cancer therapy prior to an event or for patients with an event after two or more missing tumor assessments. Patients who do not have a baseline tumor assessment or who do not have any post-baseline tumor assessments will be censored on the start date unless death occurred on or before the time of the second planned tumor assessment in which case the death will be considered an event.

The censoring and event date options to be considered for the irPFS and irDR analysis are presented in [Table 2](#).

Table 2. Outcome and Event Dates for irPFS and irDR Analyses

Scenario	Date of event/censoring	Outcome
No baseline assessment	Start date	Censored ^a
irPD (subsequently confirmed) or death ≤16 weeks after last tumor assessment or ≤16 weeks after start date	Date of first irPD or death	Event ^b
irPD (subsequently confirmed) or death >16 weeks after the last tumor assessment	Date of last adequate assessment	Censored
Treatment discontinuation due to 'Disease progression' (clinical deterioration without radiological documentation) prior to or within 12 weeks after the assessment of first irPD	Date of first irPD	Event

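### SAP 8.1.3 sets time zero for every time-to-event analysis at Cycle 1 Day 1, makes no exception for duration of response, and gives RECIST duration of response no other start date

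*SAP*

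**What the plan says.** RECIST duration of response is a Part B secondary endpoint for Cohort 3B. SAP 6.5 lists "Objective response rate (ORR) and duration of response, as assessed using the Response Evaluation Criteria in Solid Tumors (RECIST) version 1.1" but does not say when the duration starts. Protocol 2.3 also names it without a start date.

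In SAP 8.1.3, the paragraph on rPFS defines the rPFS event and then says: "Time zero for all time-to-event analyses will be defined as the first vaccination on Cycle 1 Day 1". The next paragraph opens "For duration of response per RECIST and time to response (from the first vaccination date to the time of the first response" and commits to descriptive statistics. The parenthesis in that opening defines time to response only. The paragraph continues: "Kaplan-Meier analysis may be performed if deemed necessary. These analyses may be performed for the combined cohorts 7A and 3B".

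The SAP's other two response durations do have a start:

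- irDR (10.4) is defined "as the time from first documentation of immune-related objective response (irCR or irPR) to the date of first documentation of irPD", or to death. Its formula is (date of event or censoring − first date of irOR + 1)/30.4375.
- PSA-50 duration (8.1.3): "Duration of PSA-50 response is defined as the period between the first" measurement at which the PSA-50 criterion is met and the measurement at which it no longer holds.

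The Protocol's Schedule of Activities for the expansion cohorts (tumor assessment footnote) schedules imaging every 8 weeks (±5 days), "with the first one to occur 8 weeks after C1D1 until disease progression".

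**The concern.** A Kaplan-Meier analysis of duration of response is a time-to-event analysis, so a rule for all such analyses covers it on its face. Counted from first vaccination, the clock runs before the participant has a response to lose. That stretch is event-free by construction. The result is time from first vaccination to progression or death among responders, which is a different quantity from duration of response.

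Two things would follow. Durability would look better than it is in a small cohort where a few responders determine the summary. RECIST duration and irDR in the same participant would also be measured from different origins, so a difference between them could be an artefact of the start date and not of the response criteria.

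**Working it through.** The plan states no figure for duration of response, so there is nothing to reproduce. The check has two parts.

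**Part 1: is there another start date for RECIST duration of response?**

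| Place | What it supplies |
|---|---|
| Protocol 2.3, SAP 6.5 | Endpoint named, not defined |
| Protocol 9.4 | Start for time to progression and time to response; nothing for duration |
| SAP 8.1.3, duration paragraph | Start for time to response only |
| SAP 10.3 | Defers PFS/rPFS rules to a programming specification; duration of response not named |
| SAP 10.4, closing list | Says the immune-related endpoints follow the RECIST methods, but the section reference is an unfilled placeholder (xx) |

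No visible text sets a different origin. Some of 8.1.3 is blacked out directly after the rPFS paragraph, so this finding covers the visible text only. For irDR and PSA-50 duration, a specific definition displaces the general sentence. RECIST duration has no specific definition to do so.

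**Part 2: how large is the effect if the sentence is followed literally?**

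Write R for the date of first response and E for the event or censoring date.

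E − C1D1 = (R − C1D1) + (E − R)

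The literal duration is therefore time to response plus true duration, and the excess is exactly R − C1D1. Adding 1 day, as the irDR formula does, changes both sides equally and leaves the excess unchanged.

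The first scheduled scan is at 8 weeks = 56 days, ±5 days = 51 to 61 days. Dividing by the SAP's 30.4375 days per month:

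- Response at week 8: 56/30.4375 = 1.84 months (51/30.4375 = 1.68; 61/30.4375 = 2.00)
- Response at week 16: 112/30.4375 = 3.68 months
- Response at week 24: 168/30.4375 = 5.52 months

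Two illustrative participants, with weeks chosen for the example:

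- PR at week 16, PD at week 24: true 24 − 16 = 8 weeks; literal 24 weeks; ratio 24/8 = 3.
- PR at week 8, PD at week 24: true 24 − 8 = 16 weeks; literal 24 weeks; ratio 24/16 = 1.5.

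The documents give no expected duration, so the relative effect is shown over a range of **assumed** true durations. Literal duration = true + excess; the percentage is excess/true.

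| Assumed true duration | Response at week 8 | Week 16 | Week 24 |
|---|---|---|---|
| 3 months | 4.84 (+61%) | 6.68 (+123%) | 8.52 (+184%) |
| 6 months | 7.84 (+31%) | 9.68 (+61%) | 11.52 (+92%) |
| 12 months | 13.84 (+15%) | 15.68 (+31%) | 17.52 (+46%) |

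The effect on a median was simulated under one set of **assumptions**: exponential true duration with a 6-month median, and first responses at weeks 8, 16 and 24 in 50%, 30% and 20% of responders. The mean time to response is 0.5 × 1.84 + 0.3 × 3.68 + 0.2 × 5.52 = 3.13 months. The median moves from 6.0 to about 9.3 months.

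**The case against.** The strongest reply is that nobody would apply the sentence this way. It sits in the rPFS paragraph, between the rPFS event definition and a remark that this analysis may be run on the combined cohorts, so it was probably written for rPFS. In the duration paragraph the author attaches the first-vaccination origin to time to response alone, which would be unnecessary if the earlier sentence already governed that paragraph. The SAP itself does not take *all* literally, because irDR is a censored endpoint that starts at response. SAP 10.4 also ties the immune-related endpoints to the RECIST methods, and for irDR and irPFS the only stated difference is the censoring table. A duration counted from first vaccination would contradict the endpoint's own name.

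These points stand as evidence of intent, and they limit the claim. A reader might infer that every reported RECIST duration will be inflated. The documents do not support that. Only descriptive statistics are committed, and it is debatable whether they count as time-to-event analyses. The Kaplan-Meier analysis is optional, and a programmer may well start the clock at response.

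The stakes are modest too. SAP 4.1 plans no hypothesis test. Cohort 3B has 18 participants, of whom Protocol 4.1.2 requires only about 40% (0.40 × 18 = 7.2) to have a measurable lesion, so responders may be few.

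The objection does not make the sentence correct. It relies on the programmer disregarding the plain wording, and the cross-reference that might have settled the matter is an unfilled placeholder.

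**Conclusion.** The point holds in conditional form. As worded, the rule is wrong for duration of response: it covers all time-to-event analyses without exception, the visible SAP gives RECIST duration no other start, and it conflicts with the SAP's own irDR and PSA-50 definitions.

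If it is followed for the optional Kaplan-Meier analysis (Cohort 3B, or 7A and 3B pooled), every duration carries its time to response as excess. That is about 51 to 61 days for a response at the first scheduled scan, plus about 8 weeks for each later scan. This excess is arithmetic and rests only on scans being done on schedule. The percentages and the shift in the median rest on assumed durations and response timing.

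The documents do not show that inflation will occur. ORR, rPFS, the primary safety analysis and the sample size are unaffected. This should be corrected before the analysis is programmed; it does not threaten the trial's main conclusions.

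**What to change.** In SAP 8.1.3, limit the Cycle 1 Day 1 origin to rPFS/PFS and time to response. Add that RECIST duration of response starts at the date of first documented CR or PR, for both the descriptive statistics and any Kaplan-Meier analysis, including the pooled 7A and 3B analysis. Use the form of the irDR formula:

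duration of response (months) = (date of event or censoring − first date of CR/PR + 1)/30.4375

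The cost is a sentence or two in the SAP. No data collection, sample size or test changes. Compared with the literal rule, reported RECIST durations become shorter by the time to response and share irDR's rule of starting at first documented response.

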
 
For Cohort 3B: To evaluate the anti-tumor response induced by treatment in participants with mCRPC utilizing solid tumor response criteria.
 
For Cohort 3B: To evaluate the anti-tumor response induced by treatment utilizing immune related response criteria.
 
For Cohort 3B: to evaluate bone metastatic disease outcome in participants with mCRPC.
 
For Cohorts 3B: To estimate the duration of radiographic Progression-Free Survival (rPFS) in participants with mCRPC.
 
To evaluate response rate based on 50% reduction of prostate specific antigen (PSA).
 
To evaluate PSA kinetics.
 
To evaluate trough concentrations of tremelimumab after SC administration at selected doses.
 
To evaluate trough concentrations of PF-06801591 after SC administration at selected doses.
 
To evaluate the anti-drug antibody (ADA) response of tremelimumab after SC administration with the other PrCa VBIR components.
 
To evaluate the ADA response of PF-06801591 after SC administration with the other PrCa VBIR components.
 
	
 
For Cohort 3B: Objective response rate (ORR) and duration of response, as assessed using the Response Evaluation Criteria in Solid Tumors (RECIST) version 1.1 (Appendix 3).
 
For Cohort 3B: Antitumor response and tumor control duration based on total measurable tumor burden as assessed by the Immune-Related Response Criteria Derived from RECIST 1.1 (irRECIST) (Appendix 4).
 
For Cohort 3B: Bone outcome according to Prostate Cancer Working Group 3 (PCWG3) criteria (Appendix 5).
 
For Cohort 3B: Radiographic Progression-Free Survival (rPFS) by RECIST 1.1, irRECIST and PCWG3 Criteria in participants with mCRPC.
 
PSA-50 response rate and duration of response.
 
Baseline and changes from baseline for PSA, PSA velocity, PSA slope and PSA doubling time (PSADT).
 
Trough concentrations after multiple dosing (<math>C_{trough}</math>).
 
<math>C_{trough}</math> after multiple dosing.
 
Incidence and titers of ADA and neutralizing antibodies against tremelimumab.
 
Incidence and titers of ADA and neutralizing antibodies against PF-06801591.
 

CCI	

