#### **4.1.1. Additional Inclusion Criteria for Participants with Rising PSA at High Risk for Recurrence After Definitive Local Therapy (Biochemical Relapse)**

9. Definitive loco-regional therapy for primary diagnosis including one of the following:
  - a. External radiotherapy or any salvage therapy including but not limited to brachytherapy, cryotherapy or salvage therapy;
  - b. Radical prostatectomy and radiotherapy therapy, such as external radiotherapy or brachytherapy;

- c. Prostatectomy only for participants who are not candidates for salvage therapy. Salvage therapy includes but is not limited to any of the following: any radiation therapy (such as external beam therapy, brachytherapy) or any other salvage therapy such as cryotherapy.

10. Hormone sensitive (androgen dependent) relapsing prostate cancer post definitive local therapy. Relapse is defined as a subsequent detectable PSA ( $\geq 0.2$  ng/ml) that increases on 2 or more determinations after radical prostatectomy. The values must be separated by at least 2 weeks.
11. High risk of development of metastatic disease defined as PSA doubling time less than or equal to 10 months (calculated at least 3 months before treatment administration). The PSADT calculation must include all available PSA values available over the past 6 months prior to registration using the Memorial Sloan Kettering Cancer Center (MSKCC) PSA Doubling Time Prediction Tool available at the following website: <http://nomograms.mskcc.org/Prostate/PsaDoublingTime.aspx>.
12. Male participants able to father children must agree to use one highly effective method of contraception throughout the study and for at least 90 days after the last dose of assigned treatment.
13. No concurrent use of ADT or orchiectomy. Prior use of ADT in the neoadjuvant or adjuvant setting with radiotherapy is allowed as long as it was completed at least 6 months prior to registration.
14. No evidence by imaging (of any type) of metastatic involvement as follows: loco-regional or distant lymph nodes; loco-regional or distant soft tissues; or any organ involvement, including bone.
15. Testosterone level  $\geq 150$  ng/dL.

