#### **4.1.2. Additional Inclusion Criteria for Participants in Part B Expansion Cohort 3B - After Novel Hormone Treatment (enzalutamide or abiraterone)**

16. Prior therapy with a novel hormone therapy (enzalutamide or abiraterone).
17. Testosterone levels  $< 50$  ng/dL.
18. Documented progressive disease and/or local recurrence defined by the following modified PCWG3 criteria:
  - a. PSA progression defined as a minimum of 2 consecutive rising levels, with an interval of  $\geq 1$  week between each determination. For Part B only, the last determination must have a minimal value of  $\geq 0.2$  ng/mL and be determined within two weeks prior to screening.

OR

- b. Measurable disease defined as showing new or progressive metastatic lymph node and/or local recurrence or visceral metastatic disease (with the exception of metastases to the liver) on CT or MRI scans.

OR

- c. Radionuclide bone scan with at least 2 new bone lesions.

For Part B, at least approximately 40% of the participants to be enrolled must have at least 1 measurable lesion as defined by RECIST v1.1.

19. Currently using a GnRH agonist or antagonist (unless surgically castrated).

20. Currently using a GnRH agonist or antagonist (unless surgically castrated).

21. No concurrent treatment with novel hormone therapy.

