8. STATISTICAL METHODOLOGY AND STATISTICAL ANALYSES

In general, all continuous endpoints will be summarized descriptively by cohort. If data are categorical then the standard contingency tables with counts and percent by group will be displayed.

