10.2. Appendix: PSA kinetics [Appendices](#)

PSA velocity is defined as the slope of the linear regression line of PSA against time in month.

PSA slope is the slope of the linear regression line of natural log of PSA against time in month.

PSA doubling time is defined as the natural log of 2 divided by the slope of the linear regression line of the natural log of PSA against time in month

As a numerical example

Date	PSA	Log _n	Log ₂
5/1/2016	0.5	-0.69	-1.00
6/1/2016	1	0.00	0.00
7/1/2016	0.6	-0.51	-0.74
8/1/2016	1	0.00	0.00
10/1/2016	1.6	0.47	0.68
PSA Slope	0.20	PSA Doubling Time	3.49 months
PSA Velocity	0.19 ng/ml/mo		

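### PSA doubling time is defined as ln 2 divided by the slope, with no visible rule for a flat or falling PSA, so its cohort mean and waterfall can show improvement as worsening

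*SAP*

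**What the plan says.** SAP Appendix 10.2, repeating Section 8.1.3, states: "PSA doubling time is defined as the natural log of 2 divided by the slope of the linear regression line" of ln PSA against time in months. Neither place restricts the sign or size of the slope. The one worked example has PSA rising overall.

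Three outputs draw on this quantity:

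- **Cohort means.** Section 8.1.3 says: "Mean % and absolute change from baseline in PSA kinetics may be presented by cohort". The kinetics in question are PSA, velocity, slope and PSADT. Section 8 sets a general default: "In general, all continuous endpoints will be summarized descriptively by cohort".
- **Waterfall.** Section 8.1.3 cites a PCWG3 recommendation that the percentage change in PSA and the "maximum decline in PSA, PSA velocity, PSADT and PSA slope that occurs at any point after treatment be reported for each patient" in a waterfall plot.
- **Listings and plots.** Section 8.1.3 commits to individual values by timepoint.

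Change from baseline in PSADT is a named Part B secondary endpoint (Protocol Section 2.3, SAP Section 6.5). The visible rules for special values cover titers below the detection limit (SAP 7.2), non-derivable PK parameters (7.3) and censoring of time-to-event data (7.4). None covers a negative or undefined PSADT.

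**The concern.** The reciprocal of a slope is discontinuous at zero. As a rising PSA flattens, PSADT grows without limit; once PSA starts to fall, PSADT jumps to a very large negative number. As the fall steepens, PSADT moves back towards zero from below. Arithmetic on it therefore goes wrong in three ways.

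- **Direction.** A participant whose PSA falls has a lower PSADT than any participant whose PSA rises, so the better result sits at the worse end of the scale.
- **Leverage.** The most extreme values come from near-flat slopes, where the sign is least certain. One such participant can decide the mean in a cohort of 15 to 20.
- **Waterfall.** Faster doubling and falling PSA both plot as declines in PSADT.

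Falling PSA is an expected outcome, since the same SAP section defines a PSA-50 response. The point matters most in the biochemical-relapse cohorts (1B with 20 participants, 5B with 15). There, PSA response and PSA kinetics are the visible Part B activity endpoints not restricted to Cohort 3B, and Protocol Section 3.5 bases the dose declaration for that population partly on efficacy.

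Slope and velocity do not share the defect when the baseline value is clearly positive.

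**Working it through.** **1. The SAP's own example.** Least squares on the five points in Appendix 10.2, with a month of 30.4375 days, gives a ln-PSA slope of 0.198 per month, a velocity of 0.193 ng/mL per month, and PSADT = 0.6931/0.1984 = 3.49 months. These match the stated 0.20, 0.19 and 3.49.

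**2. One participant at a time.** Biochemical-relapse entry requires the following: "High risk of development of metastatic disease defined as PSA doubling time less than or equal to 10 months". A baseline of 6 months (slope 0.6931/6 = 0.1155) is assumed here.

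| On-study slope per month | PSADT (months) | Change | What happened |
|---|---|---|---|
| 0.231 | 3 | -3 (-50%) | faster doubling |
| 0.058 | 12 | +6 (+100%) | slower doubling |
| +0.001 | +693 | +687 | almost flat |
| -0.001 | -693 | -699 | almost flat |
| -0.40 | -1.7 | -7.7 (-129%) | steep fall |

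The steep fall scores below the participant whose doubling time halved. The two almost identical flat slopes differ by 1,386 months.

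**3. How general the reversal is.** Percent change equals (on-study PSADT / baseline PSADT) - 1. With a positive baseline, every faller is below -100% and every riser above it, so the reversal is certain on this scale. On the absolute scale it is certain for a common baseline and usual otherwise. An exception is baseline 3 months then -0.40 per month: -1.7 - 3 = -4.7, which is above a worsening from 10 to 3 months at -7.0.

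**4. One participant in a cohort (assumed data).** Everyone improves: all but one slow from 6 to 12 months, and one turns to -0.005 per month.

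- That participant's change: 0.6931/(-0.005) - 6 = -144.6 months, or -2,410%.
- n = 15: (14 × 6 - 144.6)/15 = -4.0 months; (14 × 100 - 2,410)/15 = -67%.
- n = 20: (19 × 6 - 144.6)/20 = -1.5 months; (19 × 100 - 2,410)/20 = -26%.
- Mean slope change, n = 15: [14 × (0.0578 - 0.1155) + (-0.005 - 0.1155)]/15 = -0.062 per month.

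The mean turns negative when the single decliner is shallower than 0.6931/78 = 0.0089 per month (n = 15, from 14 × 6 - 6 = 78) or 0.6931/108 = 0.0064 (n = 20, from 19 × 6 - 6 = 108).

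**5. How often it might happen.** The documents give no expected slope change, so every setting below is an assumption. Each uses 20,000 simulated cohorts of 15 with normally distributed slope change. In the main case the baseline slope is normal (mean 0.12, SD 0.03), truncated below at ln 2/10 = 0.0693. The wider case uses SD 0.05 truncated at 0.02 (PSADT up to 35 months), because the SAP baseline need not be the eligibility slope.

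| Slope change: mean, SD | Negative mean PSADT change, main case | Wider baseline |
|---|---|---|
| -0.02, 0.02 | 0.3% | 17.4% |
| -0.04, 0.02 | 3.8% | 29.3% |
| -0.02, 0.04 | 14.7% | 33.9% |
| -0.04, 0.04 | 22.5% | 39.0% |
| -0.06, 0.04 | 30.7% | 44.0% |
| -0.08, 0.04 | 39.8% | 51.3% |
| -0.04, 0.08 | 49.9% | 57.3% |
| -0.08, 0.08 | 56.6% | 62.4% |
| -0.10, 0.08 | 61.0% | 66.3% |

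In the main case the mean slope improved in 97% to 100% of cohorts in every row. Adding error of SD 0.02 to the baseline slope gives 1.6% to 62%.

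**The case against.** **The outputs are not firm commitments.** The cohort mean is optional, the waterfall is reported as a PCWG3 recommendation, and the Section 8 default names no statistic. The waterfall sentence can also be read so that maximum decline applies to PSA alone. What is committed is individual listings and plots, where a negative PSADT can be read beside its negative slope. This stands and limits the weight of the point.

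**Readers would notice.** A doubling time cannot be negative, and a change of -699 months or below -100% is plainly an artefact. That is fair for extreme values. It fails for a modest mean such as -4.0 or -1.5 months, which looks plausible.

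**A rule may lie under redaction.** Parts of the SAP are blacked out, including text in Section 7 on missing values and after the Section 8.1.3 text. That is possible. The finding therefore concerns the visible text; the arithmetic does not depend on it.

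**The simulation depends on its inputs.** It does: 0.3% to 61% in the main case. With slope-change SD of 0.04 or less, an ordinary median change was negative in only up to about 7% of main-case cohorts, so a median beside the mean would often expose the problem. At SD 0.08 it would not (39% to 50%). The single-participant example and the algebra carry the argument.

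**Conclusion.** The concern holds. As written, the PSADT formula yields negative values for falling PSA and unbounded values near zero slope, and the SAP permits means, mean percent changes and a waterfall of that quantity. On percent change with a positive baseline the reversal is algebraic. How often a cohort mean would actually mislead depends on slope distributions the documents do not give.

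The consequence is modest. SAP Section 4.1 rules out hypothesis tests, so no error rate or sample size is affected. PSADT is one of several kinetics in one secondary endpoint, slope is derived alongside it, and a PSA-50 rate may be reported. It is worth correcting because a cohort summary can point the wrong way in the populations where PSA is the main visible sign of activity, and the correction is nearly free.

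**What to change.** In SAP Section 8.1.3 and Appendix 10.2:

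1. Summarise cohort change on the ln-PSA slope: mean absolute change with an interval.
2. Do not present the mean or mean percent change of PSADT.
3. Report PSADT by category, or as a median that ranks slopes of zero or below as best. Show those participants as PSA stable or declining (no doubling).
4. Replace any PSADT waterfall with one of slope change, or apply the same recoding to it.

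Two smaller additions belong with this edit. First, state which PSA values form the baseline slope. The eligibility rule has its own window ("The PSADT calculation must include all available PSA values available over the past 6 months prior to registration"), which need not be the SAP's baseline. Second, omit percent change in slope and velocity where the baseline can be near zero or negative. That is chiefly the mCRPC population: in Cohort 3B, PSA progression is one of three alternative entry criteria, another being "Radionuclide bone scan with at least 2 new bone lesions".

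The cost is SAP wording and table or figure shells; no new data or derivations are needed. The one loss is that no single mean PSADT can be quoted.
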